4.3.3 Prior and concomitant medications

Prior medications are defined as treatments taken and stopped prior to first dose of study treatment. Any medication given at least once between the day of first dose of study treatment and the last day of study visit will be considered as a concomitant medication, including those which were started before study treatment and continued during the study.

Incomplete start date of medications will be imputed (see [Appendix 2](#) for details), this will be done solely for the purpose of assigning a Study Period to the event (see Section [4.1.2](#)) and calculating MTX duration.

If stop date of the medication is clearly prior to the first administration of investigational study medication, then the medication is considered prior, otherwise concomitant. If available data is not sufficient to allow to determine if a medication ended prior to the start of study treatment, it will be considered as NOT ended before the start of study treatment. Missing end dates which are not ongoing will not be imputed, instead these entries will be more conservatively assessed as concomitant. Medications started in Follow-up period (on or after study discontinuation) will not be considered concomitant and analyzed, only listed.

For concomitant medications: if the start date is on or after the first administration in Study Period 2, then medication will be analyzed in Study Period 2 only. If the stop date is clearly before the first administration in Study Period 2, then medication will be analyzed in Study Period 1 only.

Prior and concomitant medications will be coded using WHO Drug Dictionary March 2017 Enhanced, and ATC coding.

4.3.3.1 RA medication

Frequency and percentage of patients received prior RA medication will be summarized by treatment group, Anatomical Therapeutic Chemical (ATC) classification, and PT based on SP1 FAS. Frequency and percentage of patients received concomitant RA medication will be summarized by treatment group, ATC classification, and PT for SP1, SP2, and the entire study separately. Tables will also show the total number and percentage of patients receiving at least one medication of a particular ATC classification.

All RA medication data will be listed.

4.3.3.2 Relevant non-RA medication

Relevant non-RA medication will be summarized and listed in the same way as for RA medication above.

4.4 Treatment regimen, compliance and exposure to drug

4.4.1 Extent of exposure

The extent of exposure to study treatment will be based on the total number of doses administered.

The duration of exposure to study treatment will be summarized by treatment group. In addition, the number of patients with cumulative exposure of at least certain thresholds will be summarized as follows:

- ≥ 2 weeks, ≥ 4 weeks, ≥ 8 weeks, ≥ 12 weeks, ≥ 18 weeks, and ≥ 24 weeks for SP1 and SP2 separately
- ≥ 2 weeks, ≥ 4 weeks, ≥ 8 weeks, ≥ 12 weeks, ≥ 18 weeks, ≥ 24 weeks, ≥ 30 weeks, ≥ 36 weeks, ≥ 42 weeks, and ≥ 46 weeks for the entire study

Duration variables (by Study Period and overall) will be derived as given below:

- Duration of exposure to study treatment in SP = date of last dose in SP - date of first dose in TP + 1
- Duration of observation in SP = date of last visit in SP - date of first dose in SP + 1

Date of last visit in SP1 is defined as date of first dose in SP2 if patient is treated in SP2, otherwise as a date of last visit, including End of Study visit.

Duration variables will be presented using summary statistics for continuous variables (as described in Section 2.1.2).

In addition patient exposure years will be presented for each Study Period and overall:

Patient exposure years in a period = (sum of duration of exposure in a period for all patients who received the study drug in a period) / 365.25.

Study drug administration record will be listed as collected in the eCRF.

The analysis of study treatment data will be based on the safety set.

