4.4.2 Compliance

Compliance will be calculated using dosages taken before DAS28-CRP Week 24 efficacy assessment for SP1 and before DAS28-CRP Week 48 efficacy assessment for SP2. In case of no Week 24 efficacy assessment all dosages in study period will be taken into account.

Compliance (in percent) to study drug administration in each study period will be calculated as below:

Compliance = $100 \times (\text{Number of planned doses in SP} - \text{number of missed doses in SP}) / \text{Number of planned doses in SP}$

Twelve doses of administration of study drug administration are planned for a patient in each of Study Period 1 and Study Period 2, twenty-four doses are planned for a patient in the entire study. If the patient discontinues then the expected number of doses will be adjusted using the EOS visit, i.e.

- expected number of dose = $\text{int}[(\text{date of EOS visit} - \text{date of first dose in SP}) / 14] + 1$
- where int is the integer part of the number, i.e. the number is rounded down to the next integer. For example if the difference of the dates is 13 days then the expected number of doses would be 1, while if the difference in dates is 14 days then the expected number of doses would be 2.

A missing dose of study medication is defined as a totally missing dose (where the date of study drug dose administration is missing), a dose where the full dose was not given.

A summary table will be produced showing the number and percentage of patients who missed any doses during the study period, a number of missed doses and a number of consecutive missed doses, by treatment group and in total.

In addition, compliance will be presented with counts and percentages for categories < 25%, 25 to 50%, 50 to 75% and $\geq 75\%$ compliance.

The analysis of compliance will be based on FAS.

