4.6.2.1 Adverse Event

AEs will be summarized by presenting the number and percentage of patients having any AE, by SOC and PT.

In addition, the number of events will also be presented for any AE, by primary SOC and for each PT. The average rate of adverse events will also be calculated as the number of events divided by the total number of years of exposure.

Missing and /or incomplete dates for AEs are imputed in a manner resulting in the earliest onset during the study period (see [Appendix 1](#) for details), additionally taking into account that the start date should not be after the stop date. The maximum of the earliest possible start date and the date of first administration of investigational study medication will be imputed for missing dates. If the end date is prior to the date of first administration of investigational study medication then the AE is not considered as a TEAE.

AE summary will be provided for all study periods by treatment groups and for the entire study separately. Following data will be summarized in the overall AE summary presentation.

Total number of TEAEs, patients with at least one TEAE, at least one SAE, at least one treatment related TEAE, at least one severe TEAE, at least one treatment related SAE, patients who discontinued the study due to TEAE, patients requiring study drug interruption and number of patients who died.

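### Exposure ends at the last injection but adverse events are counted for longer, so AE rates per exposure year are too high and period and overall rates are not comparable; by date, the per-period ≥ 24 weeks row is out of reach on schedule

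*SAP*

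**What the plan says.** SAP 4.4.1 gives one derivation of exposure in units of time: "Duration of exposure to study treatment in SP = date of last dose in SP - date of first dose in TP + 1". (TP for SP looks like a slip; the arithmetic is the same.) It builds exposure years from this: "Patient exposure years in a period = (sum of duration of exposure in a period for all patients", continuing with a division by 365.25. A second variable is derived alongside: "Duration of observation in SP = date of last visit in SP - date of first dose in SP + 1". For SP1 its end point is special: "Date of last visit in SP1 is defined as date of first dose in SP2 if patient is treated in SP2".

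The same section opens on another basis, "The extent of exposure to study treatment will be based on the total number of doses administered". It then lists cumulative rows in weeks, the per-period list ending "and ≥ 24 weeks for SP1 and SP2 separately" and the entire-study list ending at 46 weeks. SAP 4.4.2 states the plan: "Twelve doses of administration of study drug administration are planned for a patient in each of Study Period 1 and Study Period 2", and 24 in all.

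SAP 4.6.2.1 defines the AE rate as "calculated as the number of events divided by the total number of years of exposure", and plans AE summaries by period and for the entire study. SAP 2.3.2.1 and 4.1.2 assign an AE to SP2 if it starts on or after the day of the first SP2 dose. They keep an AE treatment-emergent until the later of leaving the study and 30 days after the last dose.

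Protocol 5.5.4 puts the last injections at Week 22 (SP1) and Week 46 (SP2), with the final visit at Week 48. Protocol 6 and 7.2.2 require only SAEs to be reported in the 30 days after participation ends.

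**The concern.** A rate per unit of time needs events and time taken from the same interval. Here the numerator runs past the last injection and the denominator does not, so every reported rate per year is raised. The lift differs between SP1, SP2 and the entire study, because the two weeks after the last SP1 dose count as exposure overall but in neither period. A reader who sets the period rates beside the overall rate, which is natural in a study with a switch at Week 24, could take a difference produced by the definitions for a change in risk.

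The threshold rows raise a separate question. If they are filled from the date formula, the top per-period row stays empty for patients who took every dose on schedule. If they are filled from dose counts, the SAP does not say how doses become weeks.

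**Working it through.** **Inputs.** Table 6-1 of the protocol sets Week w at Day 7w + 1: Week 22 is Day 155, Week 24 is Day 169 and Week 48 is Day 337. By the same rule Week 46 is Day 323. Doses are 14 days apart.

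**Planned doses reproduced.** SP1: (155 − 1)/14 + 1 = 12. SP2: (323 − 169)/14 + 1 = 12. Entire study: (323 − 1)/14 + 1 = 24. All agree with SAP 4.4.2.

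**Exposure by the SAP formula.** SP1: 155 − 1 + 1 = 155 days. SP2: 323 − 169 + 1 = 155 days. Overall, first to last dose of the study: 323 days. The periods sum to 310; the missing 13 days are Days 156–168.

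**Days over which AEs are counted.** SP1, for patients who enter SP2: Days 1–168, or 168. SP2: 337 − 169 + 1 = 169 to the Week 48 visit, or 353 − 169 + 1 = 185 to last dose + 30 days (323 + 30 = Day 353). Overall: 337 or 353.

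**Excess at a constant event rate, completers on schedule**

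| | To Week 48 visit | To last dose + 30 days |
|---|---|---|
| SP1 | 168/155 = 1.084 | 168/155 = 1.084 |
| SP2 | 169/155 = 1.090 | 185/155 = 1.194 |
| Overall | 337/323 = 1.043 | 353/323 = 1.093 |

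With an assumed true rate of 3.00 per patient-year, the first column gives 3.25, 3.27 and 3.13 for SP1, SP2 and overall. The second gives 3.25, 3.58 and 3.28.

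**Ordering of the rates.** Counting to Week 48, the overall factor (1.043) is below both period factors. Counting everything to Day 353, it lies between them (1.084 < 1.093 < 1.194). For completers the switch comes when overall event days reach 323 × 168/155 = 350.1, that is, when about 13.1 of the 16 days after the visit are captured.

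**Visit windows, counting to the last visit.** SP1: 166/157 to 170/153, or 1.06 to 1.11. SP2: 168/160 to 170/150, or 1.05 to 1.13 (±3 days on the last home dose is assumed). Overall: 334/326 to 340/320, or 1.02 to 1.06.

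**Patients who stop early.** Twelve SP1 doses without entry to SP2: 169/155 = 1.09 to the Week 24 visit, 185/155 = 1.19 to last dose + 30 days. Six doses (last on Day 71) with a final visit two weeks later: 85/71 = 1.20; to last dose + 30 days: 101/71 = 1.42.

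**Threshold rows.** 24 weeks is 168 days. Twelve on-schedule doses give 155 days, or 22.1 weeks; a 13th would give 14 × 12 + 1 = 169 days. Visit windows raise twelve doses only to 157 days in SP1 (22.4 weeks) and 160 in SP2 (22.9 weeks). A 12th dose at least 13 days late would reach 155 + 13 = 168. Counting doses × 2 weeks, 12 doses make exactly 24 weeks. The entire-study list points the other way: 24 doses give 323 days (46.1 weeks) by date, just over the 322 days of the top row, whereas 24 × 2 would be 48 weeks.

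**The case against.** The best reply is that the rate is computed as defined. Ending exposure at the last dose is a convention, and on schedule the factor is the same in both arms. That stands as a limit on importance: within-period arm comparisons are distorted only if early stopping differs between arms, and patient incidences and efficacy do not use this denominator. It does not remove the mismatch, because the same convention yields three different factors for one underlying risk.

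A reader might infer that SP2 and overall rates are too high by just 9% and 4%, and that the overall rate must fall below both period rates. The documents do not support either as a fixed result. Both rest on counting stopping at the Week 48 visit, whereas the SAP's own window runs to Day 353. On the other side, 19.4% and 9.3% assume that all AEs after the last visit reach the database, and the protocol requires only SAEs then.

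The 323 days overall are also inferred: SAP 4.4.1 prints its formulas per period only. If overall exposure were the sum of the periods, 337/310 = 1.087 would lie between the period factors. The 46-week row favours 323 but does not settle it.

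On the rows, the opening sentence about number of doses may well intend doses × 2 weeks. A reader might infer that the ≥ 24 weeks row is impossible to fill; it is not, given the dose-count reading or a late 12th dose. What remains is that the SAP does not say which measure applies, and its two lists fit different ones.

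**Conclusion.** The point holds as a minor inconsistency in the safety summaries. For completers on schedule at a constant event rate, AE rates per exposure year are too high relative to the days over which events are counted: by 8.4% in SP1, by 9.0% to 19.4% in SP2 and by 4.3% to 9.3% overall. The overall range assumes exposure from the first to the last dose of the study. For all AEs the truth is probably nearer the lower ends.

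Period and overall rates are not comparable, since 310 days of period exposure stand against 323 overall. Whether the overall rate falls below both period rates depends on how many AEs after the last visit are counted: it does for completers if few or none are, and does not if all are.

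Filled by date, the per-period ≥ 24 weeks row is empty for on-schedule completers.

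**What to change.** 1. **SAP 4.6.2.1.** Use time at risk that matches the events counted. The duration of observation in SAP 4.4.1 is already derived and serves, with one correction: as written it counts the day of the first SP2 dose in both periods (169 + 169 = 338 against 337). End SP1 observation the day before that dose, in line with SAP 4.1.2, so that 168 + 169 = 337. For the rate only, count events that start within this time. Leave the TEAE incidence tables on the SAP's TEAE definition, list events after the last visit separately, and footnote that the rate numerator therefore differs from the TEAE count. Crediting 14 days to each dose would also make the periods add up (168 + 168 = 336), but under the 30-day window it leaves 185/168 = 1.101 in SP2 and 353/336 = 1.051 overall.

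2. **SAP 4.4.1.** State one measure for the threshold rows. Either define weeks as doses × 2, keep the per-period rows and read the entire-study rows on the same basis; or keep the date formula and replace the top per-period row by a reachable one such as ≥ 21 weeks (147 days). Within visit windows (±3 days assumed for home doses), 147 days separates a last dose at the 12th dose date (at least 153 days in SP1, 150 in SP2) from one at the 11th (at most 143 and 146). State how overall exposure is derived, and write SP for TP in the formula.

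The cost is a few lines of SAP text and small programming changes. No new data are needed; the reported rates would be somewhat lower.

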4.4.2 Compliance

Compliance will be calculated using dosages taken before DAS28-CRP Week 24 efficacy assessment for SP1 and before DAS28-CRP Week 48 efficacy assessment for SP2. In case of no Week 24 efficacy assessment all dosages in study period will be taken into account.

Compliance (in percent) to study drug administration in each study period will be calculated as below:

Compliance = $100 \times (\text{Number of planned doses in SP} - \text{number of missed doses in SP}) / \text{Number of planned doses in SP}$

Twelve doses of administration of study drug administration are planned for a patient in each of Study Period 1 and Study Period 2, twenty-four doses are planned for a patient in the entire study. If the patient discontinues then the expected number of doses will be adjusted using the EOS visit, i.e.

- expected number of dose = $\text{int}[(\text{date of EOS visit} - \text{date of first dose in SP}) / 14] + 1$
- where int is the integer part of the number, i.e. the number is rounded down to the next integer. For example if the difference of the dates is 13 days then the expected number of doses would be 1, while if the difference in dates is 14 days then the expected number of doses would be 2.

A missing dose of study medication is defined as a totally missing dose (where the date of study drug dose administration is missing), a dose where the full dose was not given.

A summary table will be produced showing the number and percentage of patients who missed any doses during the study period, a number of missed doses and a number of consecutive missed doses, by treatment group and in total.

In addition, compliance will be presented with counts and percentages for categories < 25%, 25 to 50%, 50 to 75% and $\geq 75\%$ compliance.

The analysis of compliance will be based on FAS.

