### **Study Period 1 (baseline - Week 24)**

Patients will receive doses of GP2017 or US-licensed Humira® every other week during their visits at the study site in a blinded fashion. The dosage and frequency will not be changed.

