### **Study Period 2 (Week 24 - Week 48)**

At Week 24 (Visit 14) all patients with at least moderate DAS28-CRP response, as defined by EULAR response criteria (see [Table 6-3](#)) will continue or will be switched to GP2017. The dosage and frequency will not be changed.

In Study Period 2, all patients will self-administer GP2017 injections. At Week 24 (Visit 14) after appropriate training, patient will self-administer GP2017 under the supervision of qualified study personnel at study site. After being assessed as proficient at self-administration, the patient will receive written IFU for GP2017 and will continue to self-administer GP2017 injections. However, if the unblinded study team member concludes at the Visit 14 (Week 24) that the patient cannot perform self-administration as per study protocol and needs further training the patient should be invited back to the site for further training until deemed proficient.

Patients not achieving at least a moderate response will have their final assessment at Week 24 (as per assessment schedule defined for EoS/ Visit 16) and will not continue in the study.

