All doses of study treatment will be administered at the study site until Week 24. At this Visit 14 (Week 24) a patient eligible per protocol to continue in the study will be trained how to self-administer the IMP by self-administering one GP2017 injection at the site under the supervision of the unblinded qualified study personnel. If the patient is assessed as proficient at self-administration, the patient will receive IFU and 5 GP2017 pre-filled syringes for self-administration every other week until protocol Visit 15 (Week 36). However, if the unblinded team member concludes at the Visit 14 (Week 24) that the patient cannot perform self-administration as per the study protocol and needs further training the patient should be invited back to the site for further training until deemed proficient. In this case syringes assigned to the patient may continue to be stored at the site. At Visit 15 (Week 36), a patient will undergo all assessments as defined in the protocol, will perform a self-administration under supervision of unblinded site personnel at the site and subsequently will receive 5 pre-filled syringes with GP2017 for self-administration. Last self-administration will be done at Week 46. At Week 48, defined as EoS Visit, a patient will undergo all assessments as defined in the protocol. All unused syringes should be brought back to the site for the purpose of drug accountability.

All injections administered to the patient and all changes during the study must be recorded on the Dosage Administration Record CRF (eCRF).

The investigator or designated staff will instruct the patient on how to self-administer the study drug at the start of Study Period 2, and provide the patient with written instructions for use on study drug administration. The patient will receive a diary booklet to document the self-administration dates. All study administration details must be checked by site personnel and should then be transcribed from the patient diary into the eCRF at each visit in Study Period 2.

The investigator should promote compliance by instructing the patient to administer the study drug exactly as prescribed and by stating that compliance is necessary for the patient's safety and the validity of the study. The patient should be instructed to contact the investigator if he/she is unable for any reason to attend the scheduled study visit or administer the study drug as prescribed.

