#### **5.5.10 Emergency unblinding of treatment assignment**

Emergency treatment code breaks should only be undertaken when it is essential to treat the patient safely and efficaciously. Most often, discontinuation and knowledge of the possible treatment assignments are sufficient to treat a study patient who presents with an emergency condition. Emergency treatment code breaks are performed using the IRT. When the investigator contacts the system to break a treatment code for a patient, he/she must provide the requested patient identifying information and confirm the necessity to break the treatment code for the patient. The investigator will then receive details of the investigational drug treatment for the specified patient and a fax or email confirming this information. The system will automatically inform the monitor for the site and the Study lead that the code has been broken.

It is the investigator's responsibility to ensure that there is a dependable procedure in place to allow access to the IRT at any time in case of emergency. The investigator must provide oral and written information to the patient how to contact his/her backup in cases of emergency when he/she is unavailable to ensure that unblinding can be performed at any time. The investigator will provide protocol number, study treatment name if available, patient number, and instructions for contacting the local Sponsor representative (or any entity to which it has delegated responsibility for emergency code breaks) to the patient in case an emergency treatment code break is required at a time when the investigator and backup are unavailable.

Study treatment **must** be discontinued after emergency unblinding by the site. Study drug must also be discontinued for any subject whose treatment code has been broken inadvertently or for any non-emergency reason by the site. Any unblinding by the site, be it inadvertently or for non-emergency reasons, must be reported to the monitor. Patients who are prematurely unblinded will be discontinued from study treatment and requested to return 2 weeks after the last study drug intake to perform the EoS (Visit 16).

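### The expected-dose formula for discontinuing patients counts a dose on the End of Study date, so it can exceed the planned number of doses

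*SAP*

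**What the plan says.** SAP 4.4.2 fixes the full course: "Twelve doses of administration of study drug administration are planned for a patient in each of Study Period 1 and Study Period 2", and 24 over the whole study. It then departs from this for early leavers: "If the patient discontinues then the expected number of doses will be adjusted using the EOS visit". The adjusted count is int[(EoS date − first dose date in the period)/14] + 1. The example gives 1 dose at 13 days and, at the boundary, "if the difference in dates is 14 days then the expected number of doses would be 2".

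Compliance is 100 × (planned − missed)/planned. A dose is missed if its administration date is missing or the full dose was not given. Only doses before the Week 24 or Week 48 efficacy assessment enter. The results go into a by-arm table of missed doses and into four bands, the highest being 75% or more.

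On the schedule, Protocol 5.2 says "Patients will receive doses of GP2017 or US-licensed Humira® every other week" in Study Period 1. Protocol 5.5.4 places the twelfth dose of that period at Week 22 and, for Study Period 2, states "Last self-administration will be done at Week 46", with EoS at Week 48. Under Protocol 5.5.10, unblinded patients stop treatment and are "requested to return 2 weeks after the last study drug intake to perform the EoS (Visit 16"). Under Protocol 5.2, patients without a moderate response "will have their final assessment at Week 24 (as per assessment schedule defined for EoS/ Visit 16") and leave the study.

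**The concern.** By the text, EoS falls one dosing interval after the last dose, and no injection is due on that day. A formula that adds a dose as soon as the EoS date reaches a multiple of 14 days therefore counts an injection that the patient was never meant to receive. An adjustment meant to lower the expected count for early leavers can end above the full planned course.

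At stake is the accuracy of a table shown by treatment arm. A patient who received every due dose could appear in it with a missed dose and a compliance below 100%. The result could also turn on whether the final visit fell on one side or the other of a 14-day boundary.

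**Working it through.** **Inputs.** Formula, example, planned doses and bands: SAP 4.4.2. Dosing interval of 14 days: Protocol 5.2. Last doses at Weeks 22 and 46: Protocol 5.5.4. Recall at 14 days: Protocol 5.5.10. Visit window of ±2 days up to Week 24: Protocol 6.

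Let d = EoS date − first dose date in the period, and E(d) = int(d/14) + 1.

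**1. The SAP's own example.** E(13) = 0 + 1 = 1 and E(14) = 1 + 1 = 2. Both reproduce.

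**2. End of a period.** E(168) = 12 + 1 = 13, against 12 planned. Carried over the whole study, E(336) = 24 + 1 = 25, against 24. (The SAP writes the formula per period and gives no separate one for the whole study.) A Week 24 visit within its window falls at d = 166 to 170. At 166 or 167 days E = 11 + 1 = 12; at 168 to 170 days E = 13.

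**3. Unblinded patient recalled at 14 days.** With n on-schedule doses at days 0, 14, …, 14(n − 1), EoS is at d = 14n and E = n + 1, which is one too many for every n. If the last dose was a day or two early within its window, d is 14n − 1 or 14n − 2 and E = n, which is correct.

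**4. Effect on compliance in step 3.**

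- If missed = expected − received = 1, compliance is 100 × n/(n + 1):

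| Doses due and given (n) | Expected | Compliance |
|---|---|---|
| 1 | 2 | 50.0% |
| 2 | 3 | 66.7% |
| 3 | 4 | 75.0% |
| 6 | 7 | 85.7% |
| 11 | 12 | 91.7% |
| 12 | 13 | 92.3% |

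- If missed doses are taken only from dose records, missed = 0 and compliance is 100 × (n + 1 − 0)/(n + 1) = 100%.

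**5. Other gaps, on the first reading.** With EoS 13 days or less after an on-schedule last dose, E = n and compliance is 100%. With EoS 28 days after it, E = n + 2: 1/3 = 33.3% for n = 1, 3/5 = 60.0% for n = 3 and 6/8 = 75.0% for n = 6.

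**6. Testing a remedy.** Counting only due dates strictly before EoS, int[(d − 1)/14] + 1 gives 1 at 13 days, 1 at 14, 12 at 168 and 24 at 336. It is not enough alone. With one dose and EoS at 15 days it gives int(14/14) + 1 = 2, so the extra dose returns a day later. The count must also stop when study drug stops.

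**The case against.** The strongest reply is that the percentages do not follow from the SAP as written. It never defines missed doses as expected minus received. It defines a missed dose by a missing administration date or an incomplete dose, and Protocol 5.5.5 has missed injections recorded on the dosing eCRF. A patient with no such record has zero missed doses and scores 100% whatever the denominator. This stands as an open question of definition. The expected count is still wrong, and an expected dose without an administration date can fairly be read as missed.

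Second, the formula applies only to patients who discontinue, and SAP 4.2 treats anyone who completed Week 24 as having completed Study Period 1. On that reading a Week 24 non-responder keeps 12 planned doses. Protocol 5.5.9, however, lists these non-responders among those whose study drug must be discontinued. The documents leave this unsettled; the unblinding case does not depend on it.

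Third, the scope is narrow. Protocol 6 asks for other early leavers to be seen as soon as possible, and an EoS visit before the next due date is counted correctly. In Study Period 1 the scheduled visits are also dosing visits, so the 14-day boundary may have been chosen on purpose. That does not explain 13 doses against 12.

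Fourth, Table 6-1 as read from the PDF appears to mark study drug administration at Visit 16. This may be an extraction artefact. If it is real, it conflicts with the text of Protocol 5.5.4 and with the SAP's 24 planned doses, and the passages must be reconciled.

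**Conclusion.** The rule is wrong as written: it gives a count that contradicts the SAP's own plan of 12 doses per period and 24 overall. The excess is one dose when EoS falls exactly one interval after an on-schedule last dose, and more at longer gaps. Any fall in reported compliance rests on the assumption that missed doses are expected minus received. On that assumption, every patient affected enters the missed-dose table, but at a 14-day gap only those with one or two doses drop below the top band.

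Three stronger readings are tempting, and the documents do not support them:

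- That fully treated patients would be classed as non-compliant. The SAP has no such label or threshold, only descriptive bands.
- That per-protocol membership, and so the equivalence result, is affected. SAP 2.7.2 uses separate fixed dose counts in patients who completed the relevant visit, so the primary and key secondary analyses do not use this formula.
- That the arm with more early leavers will look less compliant. This needs both the subtraction reading and unequal discontinuation with late EoS visits, and neither is established.

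This is a minor correction to descriptive tables.

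**What to change.** In SAP 4.4.2, define expected doses for discontinuing patients as the number of scheduled dose dates that lie strictly before the EoS visit and not after the recorded study drug discontinuation date, capped at 12 per period and 24 for the whole study. A dose given early within its visit window should be counted under its scheduled date. Correct the worked example so that 14 days gives 1 dose.

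Add two sentences: that Week 24 non-responders have 12 planned doses in Study Period 1, and whether missed doses are expected minus received or are taken only from the dosing records. Check the Visit 16 entry for study drug in Table 6-1 against Protocol 5.5.4 and reconcile the two if the mark is real.

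The cost is a few lines of SAP text and one change to the derivation. No new data are needed, because Protocol 5.5.9 already has the date of stopping study treatment recorded in the eCRF. Made before database lock, the change needs no SAP addendum.
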